### **9.7.3 Safety analysis**

This is a NIS based on existing data. From safety information collecting and reporting perspective, this study will not involve individual medical record review, thus no adverse event/adverse drug reaction information is required to collect. The analysis refers to [Section 9.7.2](#).

## **9.8 QUALITY CONTROL**

The study will strictly follow BI standard operation procedures (SOPs). In addition, this study will follow key elements of the Guideline for GPP. The statistical analytic approach will be reviewed/repeated by a second analyst. The study report will be reviewed, approved and archived per BI SOP.

All the data cleaning, integration, and analysis will be conducted under the guidance and supervision of ZSQCC.

Greater details are documented in the NIS-DMRP.

## **9.9 LIMITATIONS OF THE RESEARCH METHODS**

This is a NIS based on existing data. Although PSM is used, we cannot rule out the influence of unmeasured confounding factors. In this study, potential limitations of the study design can be listed as:

- Zhejiang is an economically advanced province in China. Patients in this study may not be fully representative to all AIS patients in China. We plan to compare the

baseline characteristics of patients in this study with those from CSCA to evaluate the representativeness of the population in this study.

- AIS patient data from the ZSQCC platform were reported by the stroke centre without external monitoring.
- The treatment adapted for AIS patients may be different among stroke centres.
- The completeness of the captured data and potential for misclassification of data could differ among stroke centres.
- Some important variables may not be collected in the database. For example, patients' education level was not available in the database. Another example is that patients who did not receive rt-PA treatments were not followed up at 3 months after discharge. Therefore, for outcomes at 3 months we could only describe them in the rt-PA treated cohort.

## **9.10 OTHER ASPECTS**

### **9.10.1 Data quality assurance**

A quality assurance audit/inspection of this study may be conducted by the investigator or by IRBs / Independent Ethics Committee (IECs) or by regulatory authorities. The quality assurance auditor will have access to the investigator's study-related files and correspondence of this study.

### **9.10.2 Study records**

#### **9.10.2.1 Source documents**

Source documents provide evidence for the existence of the patient and substantiate the integrity of the data extracted.

#### **9.10.2.2 Direct access to source data and documents**

The investigator/institution will permit study-related audits, IRB/IEC review and regulatory inspection, providing direct access to all related database/documents. All source documents, including progress notes must be available at all times for review by the inspection by health authorities.

## **10. PROTECTION OF HUMAN SUBJECTS**

The study will be carried out in compliance with the protocol, the principles laid down in the Declaration of Helsinki, in accordance with the International Conference on Harmonisation Harmonised Tripartite Guideline for Good Clinical Practice (to the extent applicable to the NIS setting and required by local regulations), Good Epidemiological Practice, guidelines for GPP, and the relevant BI SOPs.

### **10.1 STUDY APPROVAL AND PATIENT INFORMATION**

This NIS will be initiated only after all required legal documentation has been reviewed and approved by the respective IRB/IEC and Competent Authority according to national and international regulations. The same applies for the implementation of changes introduced by amendments.

### **10.2 STATEMENT OF CONFIDENTIALITY**

Individual patient medical information obtained as a result of this study is considered confidential and disclosure to third parties is prohibited with the exceptions noted below. Patient confidentiality will be ensured by using patient identification code numbers.

Data generated as a result of the study need to be available for inspection upon request by the participating physicians, the sponsor's representatives, by the IRB/IEC and the regulatory authorities.

## **11. MANAGEMENT AND REPORTING OF ADVERSE EVENTS/ADVERSE REACTIONS**

Based on current guidelines from the International Society for Pharmacoeconomics and Outcomes Research [R11-4318] and the European Medicines Agency [R13-1970], NIS such as the one described in this proposal, conducted using health care records, do not require expedited reporting of suspected adverse events/reactions. Specifically, as stated in section VI.C.1.2.1 of Guideline on Good Pharmacovigilance Practices, Module VI – Management and Reporting of Adverse Reactions to Medicinal Products, for NIS designs, which are based on use of secondary data, reporting of adverse reactions is not required. Not applicable based on the secondary use of data without any potential that any employee of BI or agent working on behalf of BI will access individually identifiable patient data.

## **12. PLANS FOR DISSEMINATING AND COMMUNICATING STUDY RESULTS**

The rights of the investigator and of the sponsor with regard to publication of the results of this study are described in the investigator contract. As a general rule, no study results should be published prior to finalisation of the study report.

Boehringer Ingelheim intends to use data from this study to prepare peer-reviewed publications and other scientific communications such as abstracts, posters, and podiums presentations.

**ANNEX 1. LIST OF STAND-ALONE DOCUMENTS**

None.

**ANNEX 2. ENCEPP CHECKLIST FOR STUDY PROTOCOLS**

1.	Study title: Effectiveness and safety of IV rt-PA treatment in Chinese AIS patients aged above 80 years: a real-world study
2.	EU PAS Register® number:
3.	Study reference number (if applicable):

4. Section 1: Milestones	Yes	No	N/A	Section Number
1.1 Does the protocol specify timelines for				
1.1.1 Start of data collection 				6
1.1.2 End of data collection 				6
1.1.3 Progress report(s)				NA
1.1.4 Interim report(s)				NA
1.1.5 Registration in the EU PAS Register®				NA
1.1.6 Final report of study results.				6

Comments:

--

5. Section 2: Research question	Yes	No	N/A	Section Number
2.1 Does the formulation of the research question and objectives clearly explain:				7 and 8
2.1.1 Why the study is conducted? (e.g. to address an important public health concern, a risk identified in the risk management plan, an emerging safety issue)				7
2.1.2 The objective(s) of the study?				8
2.1.3 The target population? (i.e. population or subgroup to whom the study results are intended to be generalised)				9.2.2
2.1.4 Which hypothesis(-es) is (are) to be tested?				NA
2.1.5 If applicable, that there is no a priori hypothesis?				NA

Comments:

--

 Date from which information on the first study is first recorded in the study dataset or, in the case of secondary use of data, the date from which data extraction starts.

 Date from which the analytical dataset is completely available.

6. Section 3: Study design	Yes	No	N/A	Section Number
3.1 Is the study design described? (e.g. cohort, case-control, cross-sectional, other design)				9.1
3.2 Does the protocol specify whether the study is based on primary, secondary or combined data collection?				9.1 and 9.3.2
3.3 Does the protocol specify measures of occurrence? (e.g., rate, risk, prevalence)				NA
3.4 Does the protocol specify measure(s) of association? (e.g. risk, odds ratio, excess risk, rate ratio, hazard ratio, risk/rate difference, number needed to harm (NNH))				NA
3.5 Does the protocol describe the approach for the collection and reporting of adverse events/adverse reactions? (e.g. adverse events that will not be collected in case of primary data collection)				9.7.3 and 11

Comments:

7. Section 4: Source and study populations	Yes	No	N/A	Section Number
4.1 Is the source population described?				9
4.2 Is the planned study population defined in terms of:				
4.2.1 Study time period				6
4.2.2 Age and sex				9.2.2
4.2.3 Country of origin				9.2.2
4.2.4 Disease/indication				9.2.2
4.2.5 Duration of follow-up				9.4.1
4.3 Does the protocol define how the study population will be sampled from the source population? (e.g. event or inclusion/exclusion criteria)				9.2.2

Comments:

8. Section 5: Exposure definition and measurement	Yes	No	N/A	Section Number
5.1 Does the protocol describe how the study exposure is defined and measured? (e.g. operational details for defining and categorising exposure, measurement of dose and duration of drug exposure)				9.3.1

# BOEHRINGER INGELHEIM Group of Companies

## NIS Protocol

### BI Study Number 0135-0349

Page 35 of 42

c36563700-01

Proprietary confidential information © 2021 Boehringer Ingelheim International GmbH or one or more of its affiliated companies

8. Section 5: Exposure definition and measurement	Yes	No	N/A	Section Number
5.2 Does the protocol address the validity of the exposure measurement? (e.g. precision, accuracy, use of validation sub-study)				NA
5.3 Is exposure categorised according to time windows?				NA
5.4 Is intensity of exposure addressed? (e.g. dose, duration)				9.3.3
5.5 Is exposure categorised based on biological mechanism of action and taking into account the pharmacokinetics and pharmacodynamics of the drug?				NA
5.6 Is (are) (an) appropriate comparator(s) identified?				NA

Comments:

9. Section 6: Outcome definition and measurement	Yes	No	N/A	Section Number
6.1 Does the protocol specify the primary and secondary (if applicable) outcome(s) to be investigated?				9.3.2
6.2 Does the protocol describe how the outcomes are defined and measured?				9.3.2
6.3 Does the protocol address the validity of outcome measurement? (e.g. precision, accuracy, sensitivity, specificity, positive predictive value, use of validation sub-study)				NA
6.4 Does the protocol describe specific outcomes relevant for Health Technology Assessment? (e.g. HRQoL, QALYs, DALYs, health care services utilisation, burden of disease or treatment, compliance, disease management)				NA

Comments:

10. Section 7: Bias	Yes	No	N/A	Section Number
7.1 Does the protocol address ways to measure confounding? (e.g. confounding by indication)				9.7.1
7.2 Does the protocol address selection bias? (e.g. healthy user/adherer bias)				9.2.1, 9.7, and 9.9
7.3 Does the protocol address information bias? (e.g. misclassification of exposure and outcomes, time-related bias)				9.7

**BOEHRINGER INGELHEIM Group of Companies****NIS Protocol****BI Study Number 0135-0349**

Page 36 of 42

**c36563700-01**

Proprietary confidential information © 2021 Boehringer Ingelheim International GmbH or one or more of its affiliated companies

Comments:

--

11. Section 8: Effect measure modification	Yes	No	N/A	Section Number
8.1 Does the protocol address effect modifiers? (e.g. collection of data on known effect modifiers, subgroup analyses, anticipated direction of effect)				NA

Comments:

--

12. Section 9: Data sources	Yes	No	N/A	Section Number
9.1 Does the protocol describe the data source(s) used in the study for the ascertainment of:				
9.1.1 Exposure? (e.g. pharmacy dispensing, general practice prescribing, claims data, self-report, face-to-face interview)				9.3.1 and 9.4.1
9.1.2 Outcomes? (e.g. clinical records, laboratory markers or values, claims data, self-report, patient interview including scales and questionnaires, vital statistics)				9.3.2
9.1.3 Covariates and other characteristics?				9.3.3
9.2 Does the protocol describe the information available from the data source(s) on:				
9.2.1 Exposure? (e.g. date of dispensing, drug quantity, dose, number of days of supply prescription, daily dosage, prescriber)				9.3.1
9.2.2 Outcomes? (e.g. date of occurrence, multiple event, severity measures related to event)				9.3.2
9.2.3 Covariates and other characteristics? (e.g. age, sex, clinical and drug use history, co-morbidity, co-medication, lifestyle)				9.3.3
9.3 Is a coding system described for:				
9.3.1 Exposure? (e.g. WHO Drug Dictionary, Anatomical Therapeutic Chemical (ATC) Classification System)				NA
9.3.2 Outcomes? (e.g. International Classification of Diseases (ICD), Medical Dictionary for Regulatory Activities (MedDRA))				NA
9.3.3 Covariates and other characteristics?				NA
9.4 Is a linkage method between data sources described? (e.g. based on a unique identifier or other)				NA

Comments:

--

13. Section 10: Analysis plan	Yes	No	N/A	Section Number
10.1 Are the statistical methods and the reason for their choice described?				9.7
10.2 Is study size and/or statistical precision estimated?				9.5
10.3 Are descriptive analyses included?				9.7
10.4 Are stratified analyses included?				NA
10.5 Does the plan describe methods for analytic control of confounding?				9.7.1
10.6 Does the plan describe methods for analytic control of outcome misclassification?				NA
10.7 Does the plan describe methods for handling missing data?				NA
10.8 Are relevant sensitivity analyses described?				9.7.2

Comments:

--

14. Section 11: Data management and quality control	Yes	No	N/A	Section Number
11.1 Does the protocol provide information on data storage? (e.g. software and IT environment, database maintenance and anti-fraud protection, archiving)				9.8
11.2 Are methods of quality assurance described?				9.10.1
11.3 Is there a system in place for independent review of study results?				NA

Comments:

--

15. Section 12: Limitations	Yes	No	N/A	Section Number
12.1 Does the protocol discuss the impact on the study results of:				
12.1.1 Selection bias?				9.9
12.1.2 Information bias?				9.9
12.1.3 Residual/unmeasured confounding? (e.g. anticipated direction and magnitude of such biases, validation sub-study, use of validation and external data, analytical methods).				NA

**BOEHRINGER INGELHEIM Group of Companies****NIS Protocol****BI Study Number 0135-0349**

Page 38 of 42

**c36563700-01**

Proprietary confidential information © 2021 Boehringer Ingelheim International GmbH or one or more of its affiliated companies

15. Section 12: Limitations	Yes	No	N/A	Section Number
12.2 Does the protocol discuss study feasibility? (e.g. study size, anticipated exposure uptake, duration of follow-up in a cohort study, patient recruitment, precision of the estimates)				9.1 and 9.2

Comments:

16. Section 13: Ethical/data protection issues	Yes	No	N/A	Section Number
13.1 Have requirements of Ethics Committee/ Institutional Review Board been described?				10
13.2 Has any outcome of an ethical review procedure been addressed?				10
13.3 Have data protection requirements been described?				10

Comments:

17. Section 14: Amendments and deviations	Yes	No	N/A	Section Number
14.1 Does the protocol include a section to document amendments and deviations?				5

Comments:

18. Section 15: Plans for communication of study results	Yes	No	N/A	Section Number
15.1 Are plans described for communicating study results (e.g. to regulatory authorities)?				12
15.2 Are plans described for disseminating study results externally, including publication?				12

Comments:

**BOEHRINGER INGELHEIM Group of Companies****NIS Protocol****BI Study Number 0135-0349**

Page 39 of 42

**ANNEX 3. ADDITIONAL INFORMATION**

None.

2. LIST OF ABBREVIATIONS

AIS	Acute Ischaemic Stroke
ASD	Absolute Standardised Difference
BI	Boehringer Ingelheim
CDE	Centre for Drug Evaluation
CSCA	Chinese Stroke Centre Alliance
DMRP	Data Management and Review Plan
GPP	Good Pharmacoepidemiology Practice
ICH	Intracranial Haemorrhage
IEC	Independent Ethics Committee
IRB	Institutional Review Board
IV	Intravenous
IVT	Intravenous Thrombolysis
mRS	Modified Rankin Scale
NIHSS	National Institutes of Health Stroke Scale
NIS	Non-Interventional Study(ies)
PS	Propensity Score
PSM	Propensity Score Matching
RCT	Randomised Controlled Trials
RR	Relative Risk
rt-PA	Recombinant Tissue Plasminogen Activator
RWE	Real-World Evidence
SOP	Standard Operation Procedure
ZSQCC	Zhejiang Stroke Quality Control Centre

4. PURPOSE AND SCOPE

This is a complete statistical and epidemiological analysis plan for the research about whether Chinese AIS patients older than 80 years can benefit from IV rt-PA treatment within 4.5 hours of symptom onset in a real-world clinical setting, including the effectiveness and safety. More detailed and explicit statistical analysis methods and procedures are presented here, especially the Propensity Score Matching method.

5. AMENDMENTS AND UPDATES

None

6. RESEARCH QUESTION AND OBJECTIVE

Research question: Can Chinese AIS patients older than 80 years benefit from IV rt-PA treatment within 4.5 hours of symptom onset in a real-world clinical setting?

Primary objective:

- To compare the 1-year neurological functional outcome (as measured by modified Rankin Scale [mRS] score) of Chinese AIS patients aged > 80 years who received IV rt-PA treatment within 4.5 hours of symptom onset versus those who arrived or were admitted to the hospital within 4.5 hours of symptom onset and did not receive reperfusion therapy.

Secondary objectives:

- To compare in-hospital and other 1-year clinical outcomes (including any intracranial haemorrhage (ICH), all-cause mortality during hospitalisation, independence (mRS 0-2) at 1 year, distribution of mRS score at 1 year, and all-cause mortality at 1 year. Detailed description of these outcomes are provided in the section “secondary outcomes”) of elderly AIS patients who received IV rt-PA treatment within 4.5 hours of symptom onset versus those who arrived or were admitted to the hospital within 4.5 hours of symptom onset and did not receive any reperfusion therapy.
- To compare the baseline characteristics of AIS patients aged > 80 years treated with IV rt-PA within 4.5 hours of symptom onset versus AIS patients aged > 80 years who arrived or were admitted to the hospital within 4.5 hours of symptom onset and did not receive reperfusion treatment in the ZSQCC platform to evaluate potential channelling.

7. RESEARCH METHODS

7.1 STUDY DESIGN

This is a NIS based on existing data. We will analyse data of AIS patients aged > 80 years in China collected from the ZSQCC platform. [\[P2104780\]](#), [\[P2104783\]](#), [\[P2104784\]](#), [\[P2104779\]](#), [\[P2104782\]](#)

At least 1301 or 1146 AIS patients in total are planned to be enrolled to this study, calculated by 2:1 or 1:1 treatment ratio, respectively.

[figure not shown]
Patients meeting the inclusion/exclusion criteria will be divided into 2 cohorts:

- IV rt-PA cohort: AIS patients aged > 80 years who received IV rt-PA within 4.5 hours of symptom onset
- Non-reperfusion cohort: AIS patients aged > 80 years who arrived or admitted to the hospital within 4.5 hours of symptom onset and did not receive any reperfusion treatments

Propensity score matching (PSM) will be used to match the baseline characteristics between the above 2 cohorts. Clinical outcomes and baseline characteristics will be compared between the matched cohorts.

The flow of data selection for each of the 2 reporting patient cohorts is depicted in [Figure 1](#) below.

Figure 1 Patient cohorts selected for the non-interventional study

7.2 SETTING

In this study, AIS patient data from 80 stroke centres in the ZSQCC platform from January 2017 to March 2020 will be used.

7.3 STUDY POPULATION

No sampling will be undertaken and all patients who meet all the inclusion criteria and none of the patients presenting with at least one exclusion criterion will be included.

The inclusion and exclusion criteria are listed below:

Inclusion criteria:

- Patients registered in the ZSQCC platform from Jan 2017 to Mar 2020
- > 80 years of age
- Diagnosed with AIS at admission
- Arrived or admitted to the hospital within 4.5 hours of symptom onset
- If treated with IV rt-PA: received IV rt-PA within 4.5 hours of symptom onset

Exclusion criteria:

- Documented IVT contraindication except age to IV rt-PA treatment according to the SmPC.
- Missing any one of the key data (age, gender, baseline National Institutes of Health Stroke Scale [NIHSS], time of symptom onset, time of hospital arrival or admission, IVT or not, time of IV rt-PA treatment)
- Received thrombolysis agents other than rt-PA (urokinase, tenecteplase, recombinant plasminogen activator, prourokinase, streptokinase)
- Received endovascular treatment
- Received IV rt-PA after 4.5 hours of symptom onset

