### **9.2.2 Study population**

No sampling will be undertaken and all patients who meet all the inclusion criteria and none of the patients presenting with at least one exclusion criterion will be included.

The inclusion and exclusion criteria are listed below:

Inclusion criteria:

- Patients registered in the ZSQCC platform from Jan 2017 to Mar 2020
- > 80 years of age
- Diagnosed with AIS at admission
- Arrived or admitted to the hospital within 4.5 hours of symptom onset
- If treated with IV rt-PA: received IV rt-PA within 4.5 hours of symptom onset

Exclusion criteria:

- Documented IVT contraindication except age to IV rt-PA treatment according to the SmPC.
- Missing any one of the key data (age, gender, baseline National Institutes of Health Stroke Scale [NIHSS], time of symptom onset, time of hospital arrival or admission, IVT or not, time of IV rt-PA treatment)
- Received thrombolysis agents other than rt-PA (urokinase, tenecteplase, recombinant plasminogen activator, prourokinase, streptokinase)
- Received endovascular treatment
- Received IV rt-PA after 4.5 hours of symptom onset

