To account for potential confounding, the 2 cohorts will be 1:1 or 2:1 matched by baseline characteristics using the Propensity Score Matching method. The feasibility of PSM will be evaluated based on available sample size and descriptive results. If patient characteristic between the 2 cohorts are significantly different, i.e., less than 50% of patients in the IV rt-PA cohort can be matched to the non reperfusion cohort based on PSM, the study design will be re-evaluated before proceeding to analysis. The PSM aims to balance the 2 cohorts on baseline covariates. The propensity score model will include age, gender, baseline NIHSS/NIHSS categories (0-4, 5-10, 11-15, 16-21, and ≥ 22), medical insurance status, smoking status, hospital level, diabetes, coronary artery disease, atrial fibrillation, prior stroke/transient ischaemic attack, hypertension, anti-platelet, lipid lowering, oral anticoagulation, and time from symptom onset to hospital admission. The method of Nearest Neighbour matching will be used (a maximum caliper width equal to 0.2 of the standard deviation of the logit of the propensity score) to select the matched samples. Then we will compare the baseline characteristics of the 2 propensity-score-matched cohorts. The absolute standardized difference (ASD) between the 2 PS-matched cohorts will be calculated, where at least 0.1 ASD will be considered a significant difference. For baseline covariates that are not sufficiently balanced after PSM, they will be included in an appropriate multivariate model to adjust for those differences.

For the primary outcome, a comparison of the percentage of 1-year* mRS score (0-1) between the 2 PS-matched cohorts will be conducted using a Chi-square test. A conditional logistic regression model will be used to estimate odds ratios (95% confidence interval) between the 2 matched cohorts.

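### The 4.5 h limit is applied to arrival for controls but to the start of rt-PA for treated patients, so the comparator can include late arrivals with almost no chance of timely treatment, and matching removes them only in part

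*SAP*

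**What the plan says.** SAP section 7.3 and protocol section 9.2.2 list the same criteria. Every patient must have "Arrived or admitted to the hospital within 4.5 hours of symptom onset". Treated patients face a second condition: "If treated with IV rt-PA: received IV rt-PA within 4.5 hours of symptom onset". Anyone who "Received IV rt-PA after 4.5 hours of symptom onset" is excluded from both cohorts.

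SAP section 7.1 defines the comparator as "AIS patients aged > 80 years who arrived or admitted to the hospital within 4.5 hours of symptom onset and did not receive any reperfusion". No earlier arrival limit is set for it, and nothing requires that enough time remained to treat. The other relevant exclusion is "Documented IVT contraindication except age to IV rt-PA treatment according to the SmPC"; neither document says whether arriving too late counts as such a contraindication.

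SAP section 11.1 lists 15 terms for the propensity score, the last two being "oral anticoagulation, and time from symptom onset to hospital admission". Matching is nearest neighbour with "a maximum caliper width equal to 0.2 of the standard deviation of the logit of the propensity score". There is no exact match or separate caliper on time. The follow-up to the balance check reads: "For baseline covariates that are not sufficiently balanced after PSM, they will be included in an appropriate multivariate model to adjust for those differences". Reasons for non-treatment are collected, but protocol section 9.7.1 reserves them for description.

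**The concern.** For a treated patient, arrival time plus door-to-needle time must fit within 4.5 h. For a control, arrival alone must. Towards the end of the window the probability of entering the rt-PA cohort falls to practically zero, while eligibility as a control is unaffected. Propensity-score methods need every patient to have had some chance of either treatment. Here that fails by design over part of the arrival range.

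The study asks what would have happened, untreated, to patients who could be treated in time. A control ruled out by the clock says little about that. The protocol rationale also cites regulatory guidance on using real-world evidence to add populations to a label, and a comparator containing patients who could not have been treated is easy to challenge.

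**Working it through.** **1. The plan's own figures.** Inputs from protocol section 9.5: 28% v 19.2%, two-sided alpha 0.05, power 90%, loss 15%. With k treated patients per control and p̄ = (k·p1 + p0)/(k + 1), controls needed = [1.960·√(p̄(1−p̄)(1+1/k)) + 1.282·√(p1(1−p1)/k + p0(1−p0))]² / (p1−p0)².

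- k = 1: 487.2 per arm, total 974.4 (976 if each arm is rounded up). Plan: 974. 974/0.85 = 1145.9, so 1146.
- k = 2: 368.2 controls, total 1104.7 (1107 with 369 + 738). Plan: 1106. 1106/0.85 = 1301.2, so 1301.

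The sizing is sound. It implies 1146/2 = 573 controls for 1:1, or 1301/3 ≈ 434 for 2:1, out of the 1037 found in the feasibility assessment.

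**2. Chance of timely treatment by arrival time.** The documents give no door-to-needle times. Assume they are lognormal with median m and log-SD 0.4. With r minutes left to 270, P(treated in time) = Φ(ln(r/m)/0.4).

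| Arrival | r | m = 45 min | m = 60 min |
|---|---|---|---|
| 3.5 h | 60 | 76% | 50% |
| 4.0 h | 30 | 16% | 4% |
| 4.25 h | 15 | 0.3% | 0.03% |

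**3. What matching leaves.** Simulations used 1561 rt-PA patients and 1037 controls, a logistic score linear in arrival time plus other covariates, nearest-neighbour matching and the 0.2 SD caliper. Assumed: arrivals uniform over the window or skewed early, and weak or strong selection on the other covariates.

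*Broad definition:* late means arrival after 270 minutes minus the median door-to-needle time, with medians of 30, 45, 60 and 80 min.

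| | Late among controls | Late among rt-PA | Late controls retained |
|---|---|---|---|
| Before matching | 1–69% | 0.1–7% | – |
| After 1:1 | 1–37% | 0–20% | 23–100% |
| After 2:1 | 1–23% | 0–16% | 4–61% |

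Example (uniform arrivals, 45 min median, weak selection): late controls fall from 37% to about 21% with 1:1 or 8% with 2:1, against 6% and 4% of rt-PA patients. With early arrivals and a 30 min median, only 1–3% of matched controls are late.

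At this cut-off half of the patients would still be treated in time, so the upper ends overstate the share with no real chance.

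*Strict definition:* arrival after 4.0 h, medians of 45 or 60 min, 1:1. Across several sets of runs, 7–18% of matched controls were late with uniform arrivals and 1–5% with early arrivals, against under 1% of rt-PA patients.

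**4. The balance check.** In several scenarios the standardised difference for arrival time was below 0.1 although 10–23% of matched controls were late by the broad definition. In one (2:1, uniform, 30 min median, strong selection) it was 0.018 with 22% of matched controls late against 3% of rt-PA patients. In another set of runs it ranged from 0.06 to 0.20 and exceeded 0.1 in six of eight scenarios. The check sometimes flags the problem and sometimes does not.

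**5. Effect on the estimate.** With no true effect and no unmeasured confounder, the residual risk difference was at most 0.4 points (1:1) and about 1.2–1.3 points (2:1, uniform arrivals, late arrival assumed prognostic). Restricting arrival times cut the latter to about 0.3. The planned difference is 28 − 19.2 = 8.8 points.

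**6. Supply of controls.** 1037 − 573 = 464 (45%) can be lost under 1:1, and 1037 − 434 = 603 (58%) under 2:1, before matching losses. Restricting to the 99th percentile of rt-PA arrival times removed 11–37%, leaving 1037 × 0.89 ≈ 923 down to 1037 × 0.63 ≈ 653.

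**The case against.** The plan is not blind to arrival time. It is in the score, a caliper applies, and imbalance triggers adjustment. SAP section 11.1 also promises medians, quartiles and ranges, which would show a late tail if tabulated for the matched cohorts. This stands as mitigation. It does not restore overlap: other covariates can offset a late arrival in a single score, and adjustment would extrapolate to times with almost no treated patients.

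A reader might infer that matching leaves many untreatable controls in, or that the 0.1 check will pass regardless. The documents support neither. Both depend on undisclosed arrival and door-to-needle times, and the plan's first choice of 2:1 usually discards more late controls than 1:1.

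A reader might also infer that the treatment effect is seriously distorted. Nothing shows that: late controls bias the comparison only if arrival time predicts untreated outcome after NIHSS and the other covariates.

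Restriction could also leave a comparator made up more of patients whom clinicians chose not to treat. In runs with an unmeasured factor lowering both treatment and good outcome, restriction left the bias unchanged or higher (1:1: 3.8 to 3.8 and 3.4 to 3.5 points; 2:1: 2.9 to 3.3 and 2.4 to 3.4). This looks like two opposing biases no longer cancelling. It is a weak argument for keeping the late controls, but a good one for reporting both analyses.

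Finally, protocol section 9.7.2 and SAP section 11.2 are not visible, and the protocol's checklist cites 9.7.2 for sensitivity analyses. It cannot be said that the plan lacks one on this point.

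**Conclusion.** The two-clock asymmetry is explicit in both documents, and no visible criterion removes controls who arrived too late to be treated. The propensity score removes them only partly: about 1% to over a third of matched controls are late by the broad definition, and about 1–18% by the 4.0 h definition under 1:1. These ranges rest on assumed arrival patterns, door-to-needle medians of 30–80 min (45 or 60 min for the strict definition) and a score linear in time. The mean-based check is unreliable here.

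The likely bias is small against 8.8 points, so this is a flaw in how the comparator is defined and does not by itself invalidate the result. It should be corrected because the correction is cheap. If late arrival is already handled as a contraindication, or in the sections that are not visible, less remains to be done.

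**What to change.** In SAP sections 7.3 and 11.1, specify the following without looking at outcomes:

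- Before fitting the propensity score, restrict both cohorts to onset-to-arrival times within the range seen in the rt-PA cohort, for example up to its 99th percentile. Name the clock: eligibility accepts arrival or admission, while the score uses admission.
- Report how many controls this removes, and show the arrival-time distribution, not only the standardised difference, in the matched cohorts.
- Show the unrestricted analysis alongside. State now which set is primary, with no switch that depends on the matched count.
- As a further sensitivity analysis, exclude controls whose recorded reason for non-treatment is late arrival, and say whether that reason already counts as a contraindication.

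Onset, arrival or admission, and treatment times are already required key data, so nothing new has to be collected. The cost is fewer controls: 11–37% of 1037 in simulations, with matching losses on top. A harsher cut, at 270 minutes minus the median door-to-needle time, gave power after 15% loss of 94–99% (1:1) and 90–99% (2:1) with early arrivals, and 68–96% and 73–98% with uniform arrivals. The restriction is affordable unless late arrivals are very common.
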